6.4 DOCUMENTATION AFTER SURGERY

- Physical examination, vital signs, performance status
- Toxicity assessment according to NCI CTC (cf. appendix 3), especially with respect to post-surgical complications
- Additional tumor assessments, if clinically indicated.
- Pathological description of surgical results and specimen

6.5 FOLLOW-UP DOCUMENTATION

Follow-up documentation is performed in order to assess the secondary efficacy objectives of progression-free and overall survival. The follow-up programme corresponds to the guidelines of the German Cancer Society.

- Physical examination, vital signs, performance status
- Neurological examination
- Toxicity assessment according to NCI CTC (cf. appendix 3), especially with respect to late complications
- Tumor assessments, including chest X-ray (if clinically indicated), and CT of the abdomen

6.6 CRITERIA FOR EFFICACY EVALUATION

6.6.1 Tumor evaluations

Tumor measurements are to be made using the same method (e.g. physical examination, sonography, X-ray, CT scan) at each assessment. All measurable and evaluable disease should be followed until disease progression. If a patient has clinical signs of progression, then tumor evaluation can take place at that time.

All tumor evaluation is performed according to RECIST (Response Evaluation Criteria In Solid Tumors) criteria and standards (appendix 1). Confirmation of declared remissions (CR or PR) must be performed no earlier than 28 days after the original declaration of response.

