2.2 SECONDARY OBJECTIVES

Secondary endpoints are:

- Local progression-free survival
- Distant metastasis-free survival
- Overall survival
- Response rate (RECIST criteria)
- Rate of curative resections (R0)
- Rate of acute and late toxicity according to NCI CTC, and postoperative morbidity

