5.3 RADIOTHERAPY

5.3.1 Description

No prior pelvic irradiation:

Patients undergo radiotherapy once daily, 5 days a week, for 5 weeks. Patients receive 45 Gy (25 x 1.8 Gy) to the pelvis (ICRU-report 50). The pelvic radiotherapy uses a three or four field box technique and at least 6 MV photon beams. The field borders for pelvic irradiation are confined as follows:

Patients with tumors that are considered as not resectable after 45 Gy receive a 3Dconformal boost to the gross tumor volume with a security margin of 1-2 cm in every direction to a total dose of 59.8 Gy, at least. Patients with tumors that are considered as resectable receive surgery in curative intention 4-6 weeks after completion of chemoradiation.

Prior pelvic irradiation:

Patients undergo 3D-conformal radiotherapy once daily, 5 days a week, for 5 weeks. Patients receive 45 Gy (25 x 1.8 Gy) to the gross tumor volume with a security margin of 1-2 cm in each direction (ICRU-report 50). Radiotherapy uses 6 MV photon beams, at least.

Patients with tumors that are considered as not resectable after 45 Gy receive a 3Dconformal boost to the gross tumor volume with a security margin of 1-2 cm in every direction. The total dose is left to the discretion of the local radiotherapist. Patients with tumors that are considered as resectable receive surgery in curative intention 4-6 weeks after completion of chemoradiation.

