5.5 SURGICAL THERAPY

4-6 weeks after chemoradiation, tumour resection should be performed if possible and if no contraindications are present. Contraindications may be infiltration of the sacral vertebras 1 and 2 or infiltration of the basal pelvic muscles. The definite decision on further surgical treatment is left to the discretion of the local surgeon.

All surgical procedures should be performed according to the local standards of the invstigator's institution, according to established guidelines and recommendations. Surgery is not considered as an integral part of the experimental study treatment.

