6.3 ASSESSMENTS DURING AND AFTER STUDY TREATMENT

On day 1, 9, 16, 23, 30 of radiochemotherapy:

- Physical examination, vital signs, performance status
- Hematological tests: Complete blood count (CBC) including neutrophil and platelet count.
- Clinical chemistry: Sodium, potassium, calcium, creatinine, urea, bilirubin, GOT, GPT, LDH, alk. phosphatase, total protein, albumin
- Toxicity assessment according to NCI CTC (cf. appendix 3)

In addition, on day 9 and 23:

• Neurological examination

At the end of radiochemotherapy (day 35):

- Physical examination, vital signs, performance status
- Neurological examination
- 12 lead ECG (if clinically indicated).
- Hematological tests: Complete blood count (CBC) including neutrophil and platelet count.
- Clinical chemistry: Sodium, potassium, calcium, creatinine, urea, bilirubin, GOT, GPT, LDH, alk. phosphatase, total protein, albumin
- Toxicity assessment according to NCI CTC (cf. appendix 3)
- Tumor assessment by imaging techniques, corresponding to those used at baseline. Additional tumor assessments, if clinically indicated.

The above tests and procedures are summarized in the Study Flow Sheet in section 6.1.

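### RECIST responses must be confirmed at least 28 days later, but no confirmatory scan is scheduled between day 35 and surgery, so responders who are resected reach surgery unconfirmed

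*Protocol*

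**What the plan says.** RECIST response rate is a secondary endpoint (protocol, section 2.2), to be calculated with a confidence interval (section 7.2.4). Four parts of the protocol bear on how it is obtained.

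- **Confirmation (6.6.1).** "Confirmation of declared remissions (CR or PR) must be performed no earlier than 28 days after the original declaration of response". The wording is mandatory and makes no exception for patients who have surgery.
- **Scan before surgery (6.1, 6.3).** The end-of-treatment visit on day 35 includes "Tumor assessment by imaging techniques, corresponding to those used at baseline". No other tumour assessment is scheduled between baseline and surgery. Section 6.3 allows extra assessments only on clinical indication.
- **Surgery (5.5).** "4-6 weeks after chemoradiation, tumour resection should be performed if possible and if no contraindications are present".
- **After surgery (6.1, 6.4, 6.5).** The schedule table marks a tumour assessment in the post-surgery column, but CT of the abdomen is marked only before the study, on day 35 and at follow-up. Section 6.4 words the post-operative assessment as "Additional tumor assessments, if clinically indicated" and adds a pathological description of the specimen. Follow-up visits are every 3 months for the first 2 years.

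The protocol does not say how a patient is classified when the tumour is removed before a declared remission has been confirmed. It also does not say whether the reported rate counts confirmed responses only.

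**The concern.** The confirmation rule and the visit schedule are both fixed in the protocol, and for resected patients they do not fit together. A responder on day 35 who goes to surgery next meets a scheduled tumour assessment when the lesion is no longer there. Three outcomes are then possible, and each distorts the endpoint differently:

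- The response stays unconfirmed and is counted as no response. Reaching resection, which the strategy aims for, then lowers the response rate.
- A post-operative scan is accepted as confirmation. The rate then partly measures the operation.
- Some centres obtain an extra scan before surgery and others do not. Confirmation then depends on local practice and on where in the 4 to 6 week window the operation falls.

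The group exposed may not be small. The protocol's background cites resectability of up to 30% in retrospective series (1.1.2.2), R0 resection of 35% in a pre-irradiated group, and curative resection in up to 80% of patients not pre-irradiated (1.1.2.5).

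**Working it through.** The protocol gives no figure of its own to reproduce here. The check is calendar arithmetic, followed by an illustration with assumed values.

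**Inputs**
- Scan day: 35 (6.1, 6.3).
- Minimum interval to confirmation: 28 days (6.6.1).
- End of chemoradiation: day 35, when the second 5-FU infusion ends (5.1). Section 5.3.1 says "Patients undergo radiotherapy once daily, 5 days a week, for 5 weeks", so if day 1 is a Monday the last of the 25 fractions falls on day 33. Both end days are used below.
- Surgery: 28 to 42 days after the end of chemoradiation (5.5).

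**Formulas**
- Earliest confirmation = scan day + 28.
- Surgery window = end of chemoradiation + 28 to + 42.
- Slack = surgery day − earliest confirmation day.

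| End of chemoradiation | Scan | Earliest confirmation | Surgery window | Slack (days) | Window days on or after earliest confirmation |
|---|---|---|---|---|---|
| day 35 | day 35 | day 63 | 63–77 | 0 to +14 | 15 of 15 |
| day 33 | day 35 | day 63 | 61–75 | −2 to +12 | 13 of 15 |
| day 35 | day 42 (scan one week late) | day 70 | 63–77 | −7 to +7 | 8 of 15 |
| day 33 | day 42 (scan one week late) | day 70 | 61–75 | −9 to +5 | 6 of 15 |

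With the scan on day 35, surgery falls strictly later than the earliest confirmation day on 14 of 15 days (end on day 35) or 12 of 15 days (end on day 33). A valid confirmation before surgery therefore fits the calendar over most of the window. The schedule simply does not contain the scan.

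Patients who are not resected are not affected. If follow-up is counted from day 35, the first 3-monthly visit with CT is at about day 35 + 91 = day 126, well beyond the 28-day minimum.

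**Illustration of strict application (all values assumed)**

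Confirmed rate = p × (1 − r × u), where p is the day-35 response rate, r the share of responders who are resected, and u the share of those who reach surgery unconfirmed.

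- p = 50%, r = 35% (resection independent of response), u = 100%: 0.50 × (1 − 0.35) = 32.5%.
- p = 50%, r = 50%, u = 100%: 0.50 × (1 − 0.50) = 25%.
- p = 50%, r = 50%, u = 50%: 0.50 × (1 − 0.25) = 37.5%.

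The relative loss is r × u. For r from 30% to 80% and u from 25% to 100%, it runs from 0.30 × 0.25 = 7.5% to 0.80 × 1.00 = 80%. A range this wide shows that the result depends on quantities the protocol does not fix.

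**The case against.** Several stronger statements are tempting, and the protocol does not support them.

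- **A reader might infer that resected responders can never be confirmed.** The arithmetic contradicts this. There are 0 to 14 days of slack when chemoradiation ends on day 35, and section 6.3 permits extra scans on clinical indication. Confirmation is unscheduled, not impossible. It is doubtful, though, that a routine confirmation scan counts as a clinical indication, and surgery at 4 weeks leaves no room.
- **A reader might infer that the response rate is certainly biased.** The downward bias arises only if unconfirmed responders are counted as non-responders, which the text does not state. Use of a post-operative scan as confirmation is likewise possible but not prescribed.
- **A reader might take 30% to 80% as the share that cannot be confirmed.** Those background figures come from different populations and at most describe the share exposed. Section 4.1 also admits tumours already resectable at entry, so resection is not simply a marker of response.
- **A reader might infer that comparison with the cited series fails.** That would depend on the confirmation rules of publications not available here.

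It can also be said that counting rules belong in a statistical analysis plan. That is fair for the classification alone. But such a plan cannot supply a scan that the schedule never required, and dropping confirmation there would contradict a mandatory sentence in the protocol. Finally, response is one of six secondary endpoints, analysed descriptively. This limits the weight of the point but does not remove the conflict.

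**Conclusion.** The point holds in limited form. Section 6.6.1 demands confirmation at 28 days or more, while the schedule offers no tumour assessment between day 35 and resection. Followed as written, day-35 responders who are resected reach surgery unconfirmed, and their classification is undefined. Strict use of the rule would lower the response rate selectively in resected patients. Accepting post-operative imaging would score resection as response. The size of either effect cannot be derived from the protocol, and the 32.5% figure is an illustration that rests on its three assumptions.

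The feasibility endpoint, the two-stage stopping rule and the sample size do not depend on response. R0 rate and local progression-free survival do not rest on the confirmation rule either. The change is worth making because it costs little and makes a named endpoint interpretable.

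**What to change.** Amend section 6.6.1 as follows:

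- Apply the 28-day confirmation requirement only to patients who are not resected.
- For resected patients, take the response from the last scan before surgery, without confirmation.
- State that post-operative imaging does not confirm a response.
- Report the pathology of the specimen separately from RECIST response.
- Define the overall rate as best response before surgery, confirmed or not, and show the confirmed rate in non-resected patients alongside it.

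A matching sentence in section 7.2.4 would keep the analysis text consistent. Sections 6.1 and 6.4 should also agree on whether the post-surgery tumour assessment is routine or on indication.

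**Cost.** This is a change of wording with no new procedure and no change to treatment or to the timing of surgery. The scans and the pathology description are already collected. If pathology is to be summarised as a graded response, a grading must be named, because the protocol asks only for a description. The statistical price is that unconfirmed responses are a slightly softer measure; the confirmed rate in non-resected patients, shown alongside, keeps this visible.

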6.6.2 Local progression-free survival

Local progression-free survival will be defined as the time from the initial dose of radiochemotherapy to the time of locoregional disease progression or relapse (according to the TNM system) or death, or to the date of last assessment without any such event (censored observation).

6.6.3 Distant metastasis-free survival

Distant metastasis-free survival will be defined as the time from the initial dose of radiochemotherapy to the time of distant metastasis detection or death, or to the date of last assessment without any such event (censored observation).

6.6.4 Overall survival

The duration of survival will be determined by measuring the time interval from initial dose to the date of death or last observation (censored).

6.7 CRITERIA FOR SAFETY EVALUATION

6.7.1 Dose-limiting toxicity (DLT)

The following adverse reactions are defined as dose-limiting toxicity in the context of the **primary objective** of the trial to determine the feasibility rate (cf. section 7.2):

- Leukopenia or neutropenia of severity grade 3 or 4 with complications such as fever (> 38,5°C) or infection, or with a duration of > 7 days
- Thrombocytopenia of grade 3 or 4
- Non-hematological toxicity of grade 3 or 4 (except for nausea)
- Each toxicity leading to permanent discontinuation of at least one of the drugs or other treatment modalities, except for hyperthermia, if more than 60% of the scheduled applications occurred, or a delay of treatment of more than 3 weeks

6.7.2 Toxicity / adverse events (AE)

Adverse events (AE):

An adverse event (AE) is any untoward medical occurrence in a subject or clinical investigation subject administered a pharmaceutical product and which does not necessarily have a causal relationship with this treatment.

An AE can therefore be any unfavourable and unintended sign (including an abnormal laboratory finding, for example), symptom, or disease temporally associated with the use of a medicinal product, whether or not considered related to the medicinal product.

Due to regulatory requirements, events occurring during pre- and post-treatment periods should also be designated as AEs. Therefore, safety surveillance - reporting of (S)AEs - commences at the time when the subject is enrolled into the study (date of signature of the informed consent) until the End of Treatment Visit has been performed. Therefore events occurring in the period between the signed informed consent and beginning of the study drug administration are to be designated as AEs.

Adverse drug reaction (ADR):

All noxious and unintended responses to a medicinal product related to any dose should be considered adverse drug reactions (ADR). The phrase "responses to a medicinal product" means that a causal relationship between a medicinal product and an AE is at least a reasonable possibility i.e. the relationship cannot be ruled out.

Pre-existing diseases, when worsening during study therapy, have to be considered as adverse events. They can lead to serious adverse events, if they meet the criteria described in section 6.7.3.

All adverse events and toxicities are recorded continuously and reported in the Toxicity Form of the CRF (cf. section 6.7.4 for details).

6.7.3 Serious adverse events (SAE) / SUSAR

A serious adverse event (SAE) or reaction is any untoward medical occurrence that at any dose:

- Results in death
- Is life-threatening (where the patient is at immediate risk of death)

NOTE: The term "life-threatening" in the definition of "serious" refers to an event in which the subject was at risk of death at the time of the event; it does not refer to an event which hypothetically might have caused death if it were more severe.

- Requires in-patient hospitalization or prolongation of existing hospitalization
- · Results in persistent or significant disability/incapacity
- Is a congenital anomaly/birth defect or
- Is an important/significant medical event for any other reason

Medical and scientific judgment should be exercised in deciding whether expedited reporting is appropriate in cases of important medical events that may not be immediately life-threatening or result in death or hospitalization but may jeopardize the subject or may require intervention to prevent one of the other outcomes listed in the definition above. These should also usually be considered serious.

Examples of such events are intensive treatment in an emergency room, or at home for allergic bronchospasm; blood dyscrasias or convulsions that do not result in hospitalization; or development of drug dependency or drug abuse, or malignant tumors when they are histologically different from the primary tumor.

SUSARs (Suspected Unexpected Serious Adverse Reaction) represent Serious Adverse Events related to a study drug (=adverse reactions), considered "unexpected" with regard to the valid investigator's brochure or SmPC for the respective drug.

6.7.4 Methods of recording and assessing adverse events

All AEs must be documented with its NCI CTC severity grade in the appropriate toxicity section of the CRF, together with a short judgment on causality. For serious adverse events, a SAE report form (initial or follow up) must be completed in addition (cf. end of section 6.7.5 for exemptions).

The following detailed information must be recorded for each **serious** adverse event in the CRF:

- A description of the AE in medical terms, not as reported by the subject
- The date of onset (start date)
- The time of onset in case event started at the day of study drug administration (start time)
- The date of recovery (stop date)

- The time of recovery in case event stopped at the day of study drug administration (stop time)
- The grade as assessed by the investigator according to the definitions in NCI-CTC (cf. appendix 3):

Grade 1 = mild Grade 2 = moderate Grade 3 = severe

Grade 4 = life-threatening or disabling

- The causal relationship to the therapy as assessed by the investigator; the decisive factor in the documentation is the temporal relation between the AE and the study drug. The following judgments of the causality to study drug or study procedures are to be used:
 - Not Related = There is not a temporal relationship to study drug administration (too early, too late, or study drug not taken), or there is a reasonable causal relationship between another drug, concurrent disease, or circumstance and the AE.
 - Not Likely = There is a temporal relationship to study drug administration, but there is not a reasonable causal relationship between the study drug and the AE,
 - Possible = There is a reasonable causal relationship between the study drug and the AE. Dechallenge information (information referring to withdrawal of drug) is lacking or unclear.
 - Probable = There is a reasonable causal relationship between the study drug and the AE. The event responds to dechallenge (withdrawal of study drug). Rechallenge is not required.
 - Certain/Definite = There is a reasonable causal relationship between the study drug and the AE. The event responds to dechallenge and recurs with rechallenge, when clinically feasible.
- Action taken on study drug(s) (none, medication discontinued, dose reduction, medication delayed, reduction of infusion rate).
- Other action (none, concomitant medication given, new or prolonged hospitalization, procedural surgery, chemotherapy delayed, chemotherapy discontinued, chemotherapy dose reduction).
- The outcome according to the following definitions:

Recovered with sequelae.

Recovered without sequelae.

Ongoing, no therapy.

Ongoing, therapy.

Died.

Change in toxicity grade/severity.

• It must be indicated whether the SAE is the leading event, i.e. the primary medical reason for SAE reporting.

If in any one subject the same AE occurs on several occasions, then the AE in question must be documented and assessed anew each time.

Serious adverse events will be collected for 30 days after the last dose of study treatment. Serious adverse events occurring more than 30 days after a patient is discontinued from the study treatment will NOT be reported unless the investigator feels that the event may have been caused by the study drug or a protocol procedure.

6.7.5 **Procedure for reporting serious adverse events**

In the event of the occurrence of any clinical AE or abnormal laboratory test value that is serious (according to the definition provided in section 6.7.3) during the course of the study or the immediate post-treatment period, irrespective of the treatment received by the subject, the investigator is obliged to inform the investigator-sponsor **within 24 hours** by phone or fax:

[name] (LKP) Univ. Hospital Erlangen Dept. of Radiation Oncology [name] [name] Germany [contact] [contact] Email: [contact]

The immediate report by the investigator to the investigator-sponsor shall be followed by detailed, written reports using the SAE report form. The immediate and follow up reports shall identify subjects by unique code numbers assigned to the latter.

All SAEs have to be reported on the standard toxicity form of the CRF as well as on the specific SAE form including all required details.

The investigator-sponsor of the study will ensure that the legal requirements for reporting adverse events to the respective federal agency ("Bundesoberbehörde", BfArM bzw. PEI [Paul-Ehrlich-Institut]) as well as to the responsible ethical comitee(s), according to §12, Abs. 6 and § 13, Abs. 1 to 7 of GCP-V, are fulfilled.

The sponsor is obliged to inform the participating investigators about SUSARs (cf. section 6.7.3 for definition), according to the German regulations (§11, Abs. 2 and 3 of GCP-V).

Events not to be treated as SAEs:

Due to the seriousness of the disease in this study, certain conditions defined as SAEs will be excluded from expedited reporting on a SAE report form (exemptions allowed according to §12, Abs. 4, GCP-V):

- Elective hospitalization and surgery for treatment of the underlying disease
- Elective hospitalisation to simplify treatment or study procedures
- Events, including death, that are only and unequivocally caused by progression of the underlying disease

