1.1.2 Local recurrence in rectal cancer

1.1.2.1 Incidence

The incidence of local recurrence in patients with an initial diagnosis of locally advanced, stage II/III rectal cancer has decreased dramatically (to 5 - 20%) during the last decade since the introduction of total mesorectal excision and (neo)adjuvant radiochemotherapy^{2,3}. In the first German Rectal Cancer Study (CAO/ARO/AIO-94), establishing the state-of-the-art of treatment in Germany, the local recurrence rate after 5 years was as low as 6% in the group with neoadjuvant treatment, compared to 13% in the adjuvant group⁴. Nevertheless, assuming a slightly higher local failure rate outside of clinical trials, at least 2000 cases will still be diagnosed in Germany every year, with most of them having received a full radiotherapy course during primary treatment⁵.

While, in general, the prognosis is still poor, the therapeutic situation of the patient with local relapse may be a curative or a palliative one. Once isolated local recurrence is diagnosed, only a minority of patients present with resectable disease⁶. Due to the mostly intensive pre-treatment, local re-therapy has become considerably more difficult, from the points of view of technical feasibility and patient's tolerance. Most patients are in an incurable situation, often suffering from severe pain and other symptoms. Therefore, effective palliation of symptoms and preservation of a good quality of life are the major goals for most of these patients.

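### 'Not Related' in 6.7.4 does not require the study drug to be excluded as a cause, so a serious event with two plausible causes can be coded against the 6.7.2 standard and missed in SUSAR assessment and, possibly, in DLT counting

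*Protocol*

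**What the plan says.** Protocol 6.7.4 lists five causality categories among the items to be recorded for each serious adverse event. 'Not Related' has two limbs joined by 'or'. The first is the absence of a temporal relationship to the study drug. The second reads "or there is a reasonable causal relationship between another drug, concurrent disease, or circumstance and the AE". The middle category reads "Possible = There is a reasonable causal relationship between the study drug and the AE", with unclear or missing dechallenge information. 'Probable' and 'Certain/Definite' start from the same condition and add a dechallenge response and a rechallenge response respectively. For adverse events in general, 6.7.4 asks only for a short causality judgment and names no scale.

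Section 6.7.2 sets the standard for an adverse drug reaction: "a causal relationship between a medicinal product and an AE is at least a reasonable possibility i.e. the relationship cannot be ruled out".

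Two other definitions rest on that term. Section 6.7.1 opens its list with "The following adverse reactions are defined as dose-limiting toxicity". Section 6.7.3 limits SUSARs to serious events related to a study drug, which it equates with adverse reactions, and that are also unexpected. DLT is one component of the primary feasibility endpoint in 7.2.1.

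**The concern.** The categories of a causality scale should be mutually exclusive, and the scale should agree with the protocol's definition of a reaction. Here the second limb of 'Not Related' is met by any reasonable alternative cause, whether or not the study drug is also a reasonable cause. An investigator who follows the text literally can tick 'Not Related' for an event that 6.7.2 would call a reaction, and another investigator can tick 'Possible' for the same event.

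Two things depend on the result. A serious event coded 'Not Related' may not be considered as a SUSAR. It may also be left out of the DLT count, which would raise the observed feasibility rate in a single-arm trial whose stopping rule and conclusion rest on that rate. The problem arises even for pure drug toxicity, so it does not depend on how effects of irradiation or hyperthermia are attributed.

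**Working it through.** **Step 1. Apply the categories to one case.** Take a serious event that occurs during chemotherapy, has a reasonable study-drug cause (A) and also a reasonable other cause (B).

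| Rule | Condition | Met by A and B together? |
|---|---|---|
| 6.7.4 'Not Related', limb 1 | no temporal relationship | no |
| 6.7.4 'Not Related', limb 2 | B | yes |
| 6.7.4 'Not Likely' | temporal relationship, no A | no |
| 6.7.4 'Possible' / 'Probable' / 'Certain' | A, separated by dechallenge and rechallenge | yes, one of the three |
| 6.7.2 adverse drug reaction | A cannot be ruled out | yes |

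The event meets 'Not Related' and one related category. Only the related category agrees with 6.7.2, because a second plausible cause does not rule out the first.

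**Step 2. Compare with the progression exemption.** At the end of 6.7.5 an event is exempt from the SAE form only if progression is its sole and unequivocal cause. That test is stricter than limb 2. An event too uncertain for the exemption can still be coded 'Not Related'.

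**Step 3. Reproduce the design.** Inputs from 7.2.2: p0 = 0.70, p1 = 0.85, type I error 5%, power 80%, n1 = 19, rejection if 5 or more patients are non-feasible (14 or fewer feasible), total n = 59. The final cutoff is not printed. A search for the Simon optimal design with these parameters returns 14/19 and 46/59 (accept with 47 or more feasible).

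- Stop at stage 1: P(X1 ≤ 14), with X1 ~ Bin(19, p).
- Accept: Σ over x = 15 to 19 of P(X1 = x) · P(X2 ≥ 47 − x), with X2 ~ Bin(40, p).

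At p = 0.70 the acceptance probability is 0.0494 and the stage 1 stopping probability 0.718. At p = 0.85 the acceptance probability is 0.807. These agree with the stated n1, stage 1 rule, total n and error rates, so no design figure is disputed.

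**Step 4. Illustrate under-counting.** Assumptions, none of them in the protocol: true feasibility is 70%, 20 of the 30 percentage points of failure are DLTs that no other component would capture, and a share s of these is coded 'Not Related' and not counted. Scored feasibility = 1 − [0.10 + 0.20 × (1 − s)].

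| s | Scored feasibility | Stop at stage 1 | False acceptance |
|---|---|---|---|
| 0 | 70% | 71.8% | 4.9% |
| 10% | 72% | 65.0% | 9.1% |
| 20% | 74% | 57.4% | 15.5% |
| 30% | 76% | 49.4% | 24.6% |

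**The case against.** **The 6.7.2 definition governs.** DLT and SUSAR are tied to adverse reactions, not to a category of the scale, so an event with a plausible drug cause is a reaction whatever box is ticked. This is a fair reading, but the protocol never says that 6.7.2 overrides 6.7.4, nor which categories count as reactions. The contradiction stands.

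**Temporal relation is called the decisive factor in 6.7.4.** This does not settle the matter. Limb 2 is an alternative to limb 1 and applies even when the temporal relation is present.

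**The DLT link is indirect.** This largely stands. The scale is prescribed for serious events only, and the DLT bullets are triggered by grade, duration, complications, discontinuation or delay, without a causality category. Under 7.2.1, premature radiochemotherapy withdrawal or hyperthermia delivery below 80% also counts as non-feasible. A reader might infer that toxicities will drop out of the primary endpoint. The documents support only that some serious ones can.

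**The SUSAR harm is limited.** This stands in part. All SAEs go to the sponsor within 24 hours without a causality filter, although the protocol describes no reassessment of causality there. Diarrhoea and infection are listed among oxaliplatin effects in 5.2.4.3, so they are poor SUSAR candidates; the route matters for unexpected events.

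**Tumour as the other cause.** A reader might infer that most pelvic and gastrointestinal events would be explained away by the tumour. The documents do not support this. The remark in 1.1.2.1, "Most patients are in an incurable situation, often suffering from severe pain and other symptoms", describes local recurrence in general, while section 4 requires ECOG status below 2 and a life expectancy of at least 2 years and excludes chronic diarrhoea above grade 1. The protocol calls the tumour the underlying disease, so only the broad term 'circumstance' would clearly cover it. The overlap does not depend on the tumour, since any second cause is enough.

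**Conclusion.** The point holds as a conflict of definitions. For a serious event with a reasonable study-drug cause and another reasonable cause, 6.7.4 permits 'Not Related' where 6.7.2 makes it a reaction. The possible loss from SUSAR assessment follows fairly directly, softened by the unfiltered reporting of SAEs to the sponsor. The possible loss from DLT counting is weaker and confined to serious events as far as the scale itself goes; for non-serious events the protocol sets no causality categories.

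The size is unknown. The rise from 4.9% to 9.1–24.6% shows how sensitive the design is to a 2 to 6 point overstatement of feasibility. It is not an estimate for this trial: it rests on an assumed DLT share, assumed miscoding shares and a cutoff of 46/59 that the protocol does not print. Section 7.2.2 also bases the final conclusion on the confidence interval, treatment delivery and the full toxicity picture. The change is worth making because the contradiction is plain and its correction is cheap.

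**What to change.** In 6.7.4:

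- Restrict the second limb of 'Not Related' to events that another cause explains and for which a contribution of the study treatment can be ruled out, which is the 6.7.2 standard.
- State that an event with both a reasonable study-treatment cause and another reasonable cause is at least 'Possible'.
- State that 'Possible', 'Probable' and 'Certain' count as adverse reactions for 6.7.1 and 6.7.3.
- Apply the same standard to the short causality judgment on non-serious adverse events.

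The cost is one reworded definition with two or three added sentences in the protocol, and matching text on the SAE form and the toxicity page of the CRF. Sample size, treatment and visits do not change. The downside is that slightly more events will count as reactions, so the feasibility rate may come out slightly less favourable.
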